In the first-in-human phase I single-agent trial, Debio 1143 was well tolerated up to doses of 900 mg/d on Days 1-5 every 3 weeks (q3w) and up to 400 mg/d Days 1-14 q3w. The MTD was not reached for either of these schedules. The prolonged dosing schedule of Debio 1143 with a total cumulative dose of 5600 mg/cycle showed good tolerability, with an acceptable toxicity profile and treatment compliance, similar to the short-course regimen at the highest explored dose level (i.e., total cumulative dose of 4500 mg/cycle). PDy demonstration of target occupancy and linear PK were observed within the explored dose range, even at doses as low as 120 mg/d. High interpatient variability was seen, but without drug-accumulation. The dose of 200 mg/d was chosen as the RP2D when Debio 1143 was combined with both cisplatin-based chemo-radiation (100 mg/m^2 IV on Day 2 q3w) in patients with locally advanced SCCHN, and with carboplatin and paclitaxel q3w in patients with NSCLC, triple-negative breast cancer or ovarian cancer [cf. section 6.2.1.4.5 of Debio 1143 Investigator’s Brochure and (28)]. It is therefore expected that a Debio 1143 starting dose of 150 mg/d, given orally on Days 1-10 and Days 15-24 q4w, with a dose-intensity of 750 mg/week and a maximal cumulative dose of 3000 mg per cycle is tolerable, relevant in terms of biological target engagement and feasible as single agent and in combination with standard dose of nivolumab.

Given that a linear dose-effect response was not observed above 120 mg/d in the single agent mechanistic studies, and that no further PDy effects are expected when the Debio 1143 dose is increased, dose escalation beyond 200 mg/d is not planned in this study.

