4. STUDY DESIGN

4.1. GENERAL DESCRIPTION

4.1.1. PART A

Part A has an open-label, multicentre dose-optimization design applying the classical 3+3 method, aiming at optimizing the Debio 1143 dose in combination with standard doses of nivolumab (OPDIVO®) to determine the RP2D taking into account safety/tolerability and PK, as well as the treatment compliance in pre-treated patients with advanced solid malignancies.

Eligible patients will enter Part A of the study in cohorts of three evaluable patients. The starting dose of Debio 1143 will be 150 mg, daily, administered orally for 10 consecutive days every 2 weeks (i.e., Days 1-10 and Days 15-24 inclusively of each 28-day cycle [q4w]). The dose will be optimized according to the observed DLTs, patient treatment compliance, safety/tolerability and PK data, if applicable.

The DLT period is defined as Cycle 1 (i.e. lasting 4 weeks or longer in case of dosing delays). Treatment-related toxicities fulfilling DLT criteria but occurring after Cycle 1 (i.e., delayed DLTs) may also be considered for RP2D definition after discussion and agreement between the Investigators, Data Safety Monitoring Committee (DSMC) and the sponsor.

Nivolumab will be administered at 240 mg (flat dose) over at least 30 minutes as an IV infusion on Days 1 and 15 of a 28-day cycle. From Cycle 3, patients may be switched to nivolumab at a dose of 480 mg IV over at least 60 minutes on Day 1 q4w, exclusively upon Investigator request with the Sponsor agreement.

Document: T:\sas\Debiopharm\Debio_1143\CZA60507\Biostatistics\Documentation\SAP\SAP Text\V5

Author: [REDACTED] Version Number: 5.0
Version Date: 19APR2022

Template No.: CS_TP_BS016 Revision 5
Effective Date: 01Apr2018

Reference: CS_WI_BS005

Copyright © 2009, 2010, 2012, 2016, 2018 IQVIA. All rights reserved. The contents of this document are confidential and proprietary to IQVIA Holdings Inc. and its subsidiaries. Unauthorized use, disclosure or reproduction is strictly prohibited.

The maximum explored Debio 1143 dose will be 200 mg/day. Neither Debio 1143 dose escalation beyond this threshold nor any nivolumab dose increases are foreseen in this study. In individual cases of severe toxicity, the Debio 1143 dose may be reduced by a maximum of two decrements of 50 mg/day or up to a minimum dose of 100 mg/day.

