The total sample size will be between 32 (if all cohorts are futile) and 60 evaluable patients (if none of the 4 cohorts is futile). If a patient is not evaluable (i.e. not included in efficacy analysis set) he/she will be replaced.

In Part B, patients will receive Debio 1143 at the RP2D established in Part A, in combination with nivolumab at the standard dose. Per-patient dose adjustments of Debio 1143 will be considered according to the severity of any eventual observed toxicity.

Participants are planned to be treated with Debio 1143 and nivolumab for up to 52 weeks (i.e., 13 cycles, until any of the following events occurs: symptomatic progressive disease (PD), asymptomatic but confirmed PD (as per iRECIST), unacceptable toxicity (per Investigator judgment and despite up to two dose adjustments), patient withdrawal, or treatment delay greater than 4 and 8 weeks (+1 week tolerance) for Debio 1143 and nivolumab, respectively.

Permission to prolong the study treatment for one additional year can be exceptionally granted by the Sponsor, if patients are deriving continuous clinical benefit from the study treatment. Medical justification for extending the treatment and the assessment of the risk/benefit balance must be provided by the Study Investigator and will be discussed with the Sponsor. The decision to further extend study treatment will be re-evaluated on a yearly basis for each patient.

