19.1. PHARMACOKINETIC CONCENTRATIONS

Individual PK blood sample collection times, derived sampling time deviations, and plasma concentrations of Debio 1143 and Debio 1143-MET1 and serum concentrations of nivolumab will be listed and figures will be presented for Cycle 1 Day 1. Time deviations will be calculated in reference to Debio 1143 administration or nivolumab infusion as specified in Table 8-1, Table 8-2, and Table 8-3 of protocol and taking into account the windows of tolerance specified in Table 8-5 of protocol.

Time deviations (actual sampling time outside the windows of tolerance specified in Table 8-5 of protocol) will be considered only relevant and a reason for data exclusion from PK analysis in case of pre-dose concentrations. All other post-dose time deviations will be considered not relevant and therefore concentrations will always be included in the PK analysis.

Should ADA samples be analyzed for serum ADA entities, results for nivolumab ADA will be listed, and ADA concentrations will be summarized only for ADA positive samples.

For each analyte, concentrations will be summarized using descriptive statistics (described in Section 7.6) by cycle, study day and scheduled time. In addition, the summaries for nivolumab concentrations will be stratified by Nivolumab regimen (240 mg or 480 mg) as applicable and summaries for Debio concentrations will be stratified by Debio regimen (150 mg or 200 mg).

Concentrations that are missing will be omitted from the calculation of descriptive statistics.

To derive PK parameters and for summary statistics (except for calculations involving logarithmic transformations), concentrations reported as BLQ will be considered as 0 when they occur before the first quantifiable concentration. BLQ concentrations occurring after the first quantifiable concentration will be set to 1/2 LOQ.

For summary statistics where calculation involves logarithmic transformations (including geometric mean calculation), plasma levels BLQ will be set to 1/2 LOQ.

Document: T:\sas\Debiopharm\Debio_1143\CZA60507\Biostatistics\Documentation\SAP\SAP Text\V5

Author: XXXXXXXXXX Version Number: 5.0
Version Date: 19APR2022

Template No.: CS_TP_BS016 Revision 5
Effective Date: 01Apr2018

Reference: CS_WI_BS005

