Copyright © 2009, 2010, 2012, 2016, 2018 IQVIA. All rights reserved. The contents of this document are confidential and proprietary to IQVIA Holdings Inc. and its subsidiaries. Unauthorized use, disclosure or reproduction is strictly prohibited.

$t_{1/2}$, Interval	The time interval (h) of the log-linear regression to determine λ_z
$t_{1/2}$, N	Number of data points included in the log-linear regression analysis to determine λ_z .
Rsq	Goodness of fit statistic for calculation of λ_z (Regression coefficient).
%AUC _{ex}	Percentage of AUC _(0-inf) obtained by extrapolation, calculated as $[(C_{last}/\lambda_z)/AUC_{(0-inf)} \times 100]$.

The AUCs for Debio 1143, Debio 1143-MET1, and Nivolumab will be calculated using linear up/log down trapezoidal summation.

For Nivolumab AUC_{inf}, if either or both of the following criteria are not met, the corresponding AUC_{inf} value will be listed only but excluded from the summary:

- Rsq (in the calculation of λ_z) > 0.85
- %AUC_{ex} < 15.0%

For each analyte, individual PK parameters will be listed and summarized using descriptive statistics (described in Section 7.6) by cycle and study day. In Part A, the summaries will be presented for each dose level and overall. In Part B, the summaries will be presented for each cohort and overall. In addition, the summaries for nivolumab concentrations will be stratified by Nivolumab regimen (240 mg or 480 mg) as applicable.

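### Part B Debio 1143 PK parameters have no split by dose taken, and the concentration strata stop at 150 mg, so later-cycle means may mix dose levels

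*SAP*

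**What the plan says.** **Parameters (SAP 19.2).** For each analyte, "individual PK parameters will be listed and summarized using descriptive statistics (described in Section 7.6) by cycle and study day". Part A is shown by dose level and overall. For Part B, "In Part B, the summaries will be presented for each cohort and overall". The only further split in that paragraph concerns the other drug: "In addition, the summaries for nivolumab concentrations will be stratified by Nivolumab regimen (240 mg or 480 mg) as applicable".

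**Concentrations (SAP 19.1).** These are summarised by cycle, day and scheduled time, and "summaries for Debio concentrations will be stratified by Debio regimen (150 mg or 200 mg". The word *regimen* is not defined for Debio 1143.

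**Dose changes.** SAP 4.1.1 says that "the Debio 1143 dose may be reduced by a maximum of two decrements of 50 mg/day or up to a minimum dose of 100 mg/day". SAP 4.1.2 carries this into Part B: "Per-patient dose adjustments of Debio 1143 will be considered according to the severity of any eventual observed toxicity". Protocol 5.4 gives the steps as 150 and then 100 mg/d, and rules out re-escalation after a reduction.

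**Later-cycle parameters in Part B (table in SAP 19.2).** Cmax, tmax and the Cmax metabolic ratio are planned at C3D1, C3D15 and C6D1. AUC(0-4h) and its metabolic ratio are planned at C3D1 only. Trough concentration is planned in Cycle 1 only (days 8 and 22).

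**The concern.** PK disposition of Debio 1143 is a secondary objective of Part B. The planned tables put Cycle 1, Cycle 3 and Cycle 6 values of the same parameter side by side, which invites a comparison over time. Once reduced, a patient's dose cannot go back up, so the mix of doses at a later visit can only shift downward within the patients still sampled. A lower Cycle 3 or Cycle 6 mean in a cohort column could then reflect dose reductions alone, and the table would not show it.

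The SAP already applies the needed principle to nivolumab. It stratifies by 240 or 480 mg and restricts several Cycle 3 nivolumab parameters to patients on the 240 mg dose. It makes no matching provision for Debio 1143, the only one of the two drugs whose dose may be reduced.

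**Working it through.** No planned figure exists to reproduce, so the check is a reading of the text followed by dose-mix arithmetic.

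**1. Dose levels against strata.** SAP 16.1 sets the planned dose per cycle at 20 × 200 = 4000 mg, which implies 200 mg/day. Two 50 mg steps give 200 − 50 = 150 and 200 − 100 = 100 mg/day. Three dose levels are possible, against two concentration strata and no parameter stratum in Part B.

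**2. The two readings of *regimen* in SAP 19.1.**
- Actual dose: records at 100 mg have no stratum.
- Assigned dose: with a Part B dose of 200 mg, every Part B patient stays in the 200 mg stratum after a reduction, so the concentration summaries mix doses as well.

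**3. Exclusions.** SAP 19 removes data that are invalid, for example through deviations or sample-processing errors. A permitted dose reduction is not among these grounds, so post-reduction values stay in.

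**4. Size.** Inputs:
- Starting dose 200 mg/day (SAP 16.1).
- Reduced dose d of 150 or 100 mg/day (SAP 4.1.1, protocol 5.4).
- Linear PK: protocol 5.3 reports for the single-agent trial that "linear PK were observed within the explored dose range". Carrying this over to the combination is an assumption.
- Share f of sampled patients on the reduced dose: not in the documents; assumed range 10% to 50%.

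Under linear PK a patient on dose d has d/200 of the exposure that he or she would have on 200 mg. Relative to everyone on 200 mg:
- fall in geometric mean = 1 − (d/200)^f
- fall in arithmetic mean = f × (1 − d/200)

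| f | 150 mg: geometric / arithmetic | 100 mg: geometric / arithmetic |
|---|---|---|
| 10% | 2.8% / 2.5% | 6.7% / 5.0% |
| 20% | 5.6% / 5.0% | 12.9% / 10.0% |
| 30% | 8.3% / 7.5% | 18.8% / 15.0% |
| 50% | 13.4% / 12.5% | 29.3% / 25.0% |

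In counts for one cohort at one visit, with all others on 200 mg:
- 2 of 8 on 100 mg: 1 − 0.5^(2/8) = 15.9%
- 2 of 15 on 100 mg: 1 − 0.5^(2/15) = 8.8%
- 2 of 8 on 150 mg: 1 − 0.75^(2/8) = 6.9%

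**5. After the change.** Dividing each value by the dose taken, or summarising within dose, makes this artificial fall 0% under linear PK.

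**The case against.** The strongest reply is that the information is not lost. If *regimen* means the dose taken, SAP 19.1 lets a reader follow the 200 mg concentrations from Cycle 1 to Cycle 6. In Part B, C3D15 and C6D1 have only pre-dose and 1.5 h samples, so Cmax there is simply the larger of two concentrations that 19.1 already stratifies. Individual parameters and exposure data are listed, and individual profiles are plotted. Protocol 11.4.1.3 plans a population PK analysis, and both documents define the secondary PK endpoint through the population model. This stands as mitigation. It does not settle the point: *regimen* is undefined, 100 mg has no stratum on the favourable reading, and SAP 19.2 makes the population analysis conditional and reports it elsewhere, so the cohort tables remain unlabelled for dose.

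It is also fair that reductions may be rare among patients sampled at Cycle 3 or 6, that 100 mg requires two reductions from 200 mg, and that the high interpatient variability reported in protocol 5.3 could hide a fall of this size. SAP 4.3 records futility of the Part B cohorts, so later-cycle groups will be small. Splitting each cohort by three doses would leave very few patients per cell. This bears on the form of the remedy.

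The documents do not support four stronger readings:
- A reader might infer that trough and Cycle 6 AUC are affected too. Neither is planned for Part B at those visits, and the metabolic ratios are largely independent of dose under linear PK.
- A reader might infer that a dose effect could never be separated from a change over time. The listings and 19.1 allow at least a partial separation.
- A reader might infer that the protocol expects Debio 1143 to alter its own exposure through CYP 3A4/5. Protocol section 3 raises CYP effects in order to restrict co-medication, calls their clinical relevance unknown, and does not say that CYP 3A clears Debio 1143.
- A reader might infer that a drop will appear. It appears only if patients on a reduced dose are sampled.

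**Conclusion.** The point holds as a small reporting gap in a secondary PK analysis. SAP 19.2 gives Part B Debio 1143 and MET1 parameters no dose split and no normalisation, and SAP 19.1 lacks a 100 mg stratum and a definition of the one it uses. The affected quantities are Cmax at C3D1, C3D15 and C6D1, and AUC(0-4h) at C3D1.

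The artificial fall in the geometric mean is about 3% to 13% if the reduced patients take 150 mg and 7% to 29% if they take 100 mg. These figures rest on a 200 mg starting dose, linear PK in the combination, and an assumed 10% to 50% of sampled patients reduced. The direction follows from the bar on re-escalation; the size cannot be fixed from the documents. The primary endpoint is untouched, and no dosing rule is in question.

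**What to change.** - **SAP 19.1:** define the Debio 1143 stratum as the actual dose taken on the sampling day, and add a 100 mg stratum.
- **SAP 19.2:** in the Part B cohort and overall columns, show dose-normalised Cmax and AUC(0-4h) for Debio 1143 and MET1. Alternatively, summarise these parameters by actual dose for Part B overall.

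Dose normalisation keeps all patients in one column and so avoids the sparse cells. Its meaning depends on linearity, so the un-normalised values should stay in the listings with the dose shown.

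The cost is a few sentences and one grouping variable. The administered dose by date is already recorded and used for cumulative dose in SAP 15.1. The downside is that some dose strata will hold few patients.

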19.3. EXPLORATORY PHARMACOKINETIC ANALYSES

The correlations between Debio 1143 PK parameters and efficacy/safety parameters will be produced in an exploratory manner. Analyses of correlation between various Debio 1143 PK parameters with clinical response, QTcF and selected lab parameter grades are described below.

Debio 1143 PK parameters vs. Clinical response

Boxplots will be produced where the y-axis displays the value of C_{max} at Cycle 1 Day 1. The x-axis will display each level of confirmed objective response as described in section 17.1.1. Similarly, the box plots will be produced for each level of cBOR as described in section 17.2.1.3. Finally, a scatter plot with a fitted regression line will be produced, with the x-axis presenting the value of C_{max} at Cycle 1 Day1 and the y-axis presenting the best change in tumor size (lowest percentage change from baseline in SOLD).

The analysis described above will be repeated for the following parameters: C_{max} at Cycle 1 Day 8 and C_{trough} at Cycle 1 Day 8.

Debio 1143 PK parameters vs. QTcF

Document: T:\sas\Debiopharm\Debio_1143\CZA60507\Biostatistics\Documentation\SAP\SAP Text\V5	Version Number: 5.0
Author: ██████████	Version Date: 19APR2022
Template No.: CS_TP_BS016 Revision 5	Reference: CS_WI_BS005
Effective Date: 01Apr2018	

A scatter plot with a fitted regression line will be produced, with the y-axis presenting the absolute QTcF value at Cycle 1 Day 1/0.5 – 2 hours post-dose and the x-axis presenting the value of C_{max} at Cycle 1 Day 1. Horizontal dashed lines will be added for each of the markedly abnormal criteria for QTcF as described in section 18.4.1. Similarly, the same regression plot will be produced except for the relative change from baseline in QTcF.

The analysis described above will be repeated for the following:

- C_{max} at Cycle 1 Day 1 vs. QTcF at cycle 1 day 1/4 – 6 hours post-dose
- C_{max} at Cycle 1 Day 1 vs. change from baseline in QTcF at cycle 1 day 1/4 – 6 hours post-dose
- C_{max} at Cycle 1 Day 8 vs. QTcF at cycle 1 day 8/0.5 – 2 hours post-dose
- C_{max} at Cycle 1 Day 8 vs. change from baseline in QTcF at cycle 1 day 8/0.5 – 2 hours post-dose
- C_{max} at Cycle 1 Day 8 vs. QTcF at cycle 1 day 8/4 – 6 hours post-dose
- C_{max} at Cycle 1 Day 8 vs. change from baseline in QTcF at cycle 1 day 8/4 – 6 hours post-dose
- $MR_{C_{max}}$ at Cycle 1 Day 1 vs. QTcF at cycle 1 day 1/0.5 – 2 hours post-dose
- $MR_{C_{max}}$ at Cycle 1 Day 1 vs. change from baseline in QTcF at cycle 1 day 1/0.5 - 2 hours post-dose
- $MR_{C_{max}}$ at Cycle 1 Day 1 vs. QTcF at cycle 1 day 1/4 – 6 hours post-dose
- $MR_{C_{max}}$ at Cycle 1 Day 1 vs. change from baseline in QTcF at cycle 1 day 1/4 – 6 hours post-dose
- $MR_{C_{max}}$ at Cycle 1 Day 8 vs. QTcF at cycle 1 day 8/0.5 – 2 hours post-dose
- $MR_{C_{max}}$ at Cycle 1 Day 8 vs. change from baseline in QTcF at cycle 1 day 8/0.5 – 2 hours post-dose
- $MR_{C_{max}}$ at Cycle 1 Day 8 vs. QTcF at cycle 1 day 8/4 – 6 hours post-dose
- $MR_{C_{max}}$ at Cycle 1 Day 8 vs. change from baseline in QTcF at cycle 1 day 8/4 – 6 hours post-dose

Debio 1143 PK parameters vs. Lab Parameter Grades

Boxplots will be produced where the y-axis displays the value of C_{max} at Cycle 1 Day 1. The x-axis will display the maximum grade in AST experienced during Cycles 2 and 3 combined. This will be repeated for the following parameters ALT, bilirubin, amylase and lipase and for the value of C_{max} at Cycle 1 Day 8.

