If a patient does not meet the requirements for treatment continuation on any day other than D1 (D2-10 or D15-24) of any cycle, treatment will be immediately interrupted and the corresponding Debio 1143 dose (and nivolumab if on D15) will be omitted. Patients should be re-assessed, ideally, every 48-72 hours, if clinically indicated, and treatment will only be resumed after all re-treatment criteria are met. On D1, treatment can be delayed more than 3 days if required; in this case, the assessment schedule will shift accordingly, and all assessments planned for D1 will be performed on the day treatment is re-started. However, if treatment is interrupted during any day other than D1 and the re-treatment criteria are not met within 72 hours, treatment will be resumed only on D1 of the next cycle.

A maximum delay of 4 and 8 weeks (+1-week tolerance) for Debio 1143 and nivolumab, respectively, is allowed. After this delay-period, treatment will be withdrawn. Patients withdrawing from treatment for any reason will be followed for safety up to 5 months (±15 days) after the last nivolumab infusion, complete resolution or stabilization of any ongoing toxicity, unless the patient starts a new treatment, end-of-life-care or withdraws consent.

Patients experiencing immune-related AEs, that require withholding nivolumab infusions temporarily until resolution to at least Grade 1, may withhold nivolumab for a maximal period of up to 8 weeks (±1 week

tolerance). During this period, patients may continue to receive Debio 1143 as per protocol, if appropriate. Patients requiring more than 8 weeks ( $\pm 1$  week) of nivolumab interruption and those who permanently discontinue nivolumab for any reason, will discontinue Debio 1143 permanently and will be withdrawn from the study. The nivolumab dose will not be adjusted under any circumstances.

Patients experiencing any treatment-related grade 4 toxicity (clinically or laboratory, excluding grade 4 amylases and/or lipase and/or non-febrile neutropenia) will withdraw from treatment definitively without further reduction (see [section 8.3.2.1](#) for details).

Patients experiencing any other treatment-related toxicity fulfilling applicable DLT criteria (as shown below) at any time during the study must stop treatment and may only resume treatment after adequate recovery to re-treatment criteria.

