### 8.1.3. Exploratory endpoints

Exploratory endpoints are:

- Potential predictive and PDy biomarkers of Debio 1143 combined with nivolumab, in blood and tumor tissue [REDACTED]
- Best overall response (BOR) evaluation using the novel iRECIST 2017 guideline for immunotherapeutics
- Correlations between PK disposition of Debio 1143 combined with nivolumab and clinical response and/or any tumor metrics
- Correlations between PK disposition of Debio 1143 combined with nivolumab and safety profile, and PDy if applicable
- Correlations between Debio 1143 and Debio 1143-MET1 plasma concentrations and changes from baseline QTcF.
- Correlations between response, clinical parameters, immune correlates and putative biomarkers, [REDACTED]
- Genetic variations in DMET genes associated with differences in the PK disposition of Debio 1143 in combination with nivolumab.

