#### 8.2.2.5. Safety laboratory

Safety laboratory measurements are scheduled at screening, C1D1 pre-treatment (only required if screening test were performed > 7 days prior to C1D1 or if inclusion/exclusion criteria were not met during screening),

on Days 3 (Part A only), 8, 15, 17 (Part A only), and 22 of Cycle 1, on Days 1 and 15 of Cycle 2 and 3, on Days 1 of any other subsequent cycle and at EOT. On dosing days, samples will always be collected predose and results reviewed prior to nivolumab infusion, if applicable. All measurements will be performed locally.

On Days 3 and 17 of Cycle 1 for patients included in Part A only, serum will be collected and measured for total bilirubin (if >ULN: direct bilirubin should also be measured), alkaline phosphatase (ALP), AST, ALT and creatinine.

For all other visits mentioned above, blood/serum will be measured for the following panels:

- **Hematology:** Hemoglobin, hematocrit, complete blood count (incl. differential) and platelets
- **Chemistry:** Creatinine, sodium, potassium, calcium, total bilirubin (if >ULN: direct bilirubin should also be measured), ALP, AST, ALT, amylase, lipase, lactate dehydrogenase (LDH), total protein, albumin and C-reactive protein (CRP)

In addition, the following laboratory measurements will be collected:

- on Days 1 and 15 of Cycle 1 and Days 1 of each subsequent cycle:

TSH, free triiodothyronine (FT3), free thyroxine (FT4),

- At screening, the following will also be measured: HIV, HBV, and HCV serology, CPK and troponins, FSH/LH and total testosterone (in males) or estrogens (in pre-menopausal female patients, meaning those whose last menstruation occurred within 12 months of screening date), free-cortisol (at morning) and ACTH. These dosages could be repeated if clinically indicated.

For applicable patients included in Cohort 4, CA-125 dosages will be performed at screening within 4 weeks of C1D1 and will be repeated on Day 1 of each subsequent cycle, if abnormally elevated levels are obtained before treatment start. Patients are evaluable as per GCIG criteria only if they have a pretreatment sample that is at least twice the upper limit of the reference range and within 2 weeks before starting the treatment.

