### 11.6.4.5. Pharmacokinetics

PK concentrations will be presented by timepoint and by dose (Part A) and overall and by cohort (Part B) as descriptive statistics for Debio 1143 and Debio 1143-MET1.

Descriptive statistics will include the number of patients, arithmetic mean, standard deviation, minimum, median, maximum, CV%, geometric mean, standard deviation of the geometric mean, geometric CV%, and 90% CI of geometric mean.

Graphic displays of plasma concentration vs. time curves will be presented individually by patient and as arithmetic means  $\pm$  arithmetic standard deviations using linear/linear scales and as geometric means  $\pm$  geometric standard deviations using log10/linear scales.

PK parameters will be listed by patient and summarized as descriptive statistics.

PK data will be presented similarly for nivolumab, when applicable.

The relationship between PK disposition and clinical response, PDy, QTcF variations, safety and genetic variations in DMET genes will be analyzed by regression methods or association analyses.

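### SAP 19.3 relates Debio 1143 Cmax to liver and pancreatic laboratory grades in Cycles 2–3 only; this omits Cycle 1 and may weaken an early exposure–toxicity relation

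*SAP*

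**What the plan says.** SAP 19.3 says that analyses of "correlation between various Debio 1143 PK parameters with clinical response, QTcF and selected lab parameter grades are described below". For the laboratory part, box plots put Cmax at Cycle 1 Day 1 on the y-axis and "the maximum grade in AST experienced during Cycles 2 and 3 combined" on the x-axis. It continues: "This will be repeated for the following parameters ALT, bilirubin, amylase and lipase", and again for Cmax at Cycle 1 Day 8. That is 5 parameters × 2 Cmax values = 10 plots per study part. No reason is given for the Cycles 2–3 window, it is not among the changes from protocol in SAP 4.3, and no rule covers patients without a Cycle 2–3 value.

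The endpoint being served has no cycle limit: "Correlations between PK disposition of Debio 1143 combined with nivolumab and safety profile, and PDy if applicable" (Protocol 8.1.3). SAP 3.3 marks the endpoints deferred to a separate analysis plan, and this one is not marked.

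The QTcF plots in the same section do use Cycle 1 outcomes, with "the y-axis presenting the absolute QTcF value at Cycle 1 Day 1/0.5" to 2 hours after dosing, and likewise on Day 8.

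**The concern.** Exposure is measured in Cycle 1, which is also the DLT period and has the densest liver sampling in Part A, yet laboratory outcomes are read only from Cycle 2 onward. A patient with high Cmax who stops in Cycle 1 because of liver toxicity has no point on the plot. One who is held or dose-reduced appears with a later grade, still plotted against the Cmax measured before the change.

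These are the drug's named risks. Transaminase elevation with raised bilirubin, and marked lipase or amylase elevation, are Debio 1143 events of special interest (Protocol 9.1.6). ALT elevation was the only treatment-related reason for discontinuation in the first-in-man study (Protocol 2.3). A flat plot could be read as evidence that exposure does not drive these changes when the window contributed to the flatness.

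**Working it through.** The plan attaches no sample size or precision figure to these plots, so there is nothing of its own to reproduce.

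**1. Scheduled draws outside the window.** Protocol 8.2.2.5 schedules post-dose safety laboratory samples "on Days 3 (Part A only), 8, 15, 17 (Part A only), and 22 of Cycle 1", then on Days 1 and 15 of Cycles 2 and 3. The Day 3 and Day 17 panel contains AST, ALT and bilirubin but not amylase or lipase. Share omitted = Cycle 1 draws / (Cycle 1 draws + Cycle 2–3 draws).

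| Parameter set | Cycle 1 | Cycles 2–3 | Omitted |
|---|---|---|---|
| Liver, Part A | 5 (D3, 8, 15, 17, 22) | 4 | 5/9 = 56% |
| Liver, Part B | 3 (D8, 15, 22) | 4 | 3/7 = 43% |
| Amylase/lipase, both parts | 3 (D8, 15, 22) | 4 | 3/7 = 43% |

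Dosing-day samples are taken before the dose, so the Day 8 sample precedes the Day 8 Cmax. Counting only draws after that dose, the Day 8 plots omit 3/(3+4) = 43% of liver draws in Part A, and 2/(2+4) = 33% of liver draws in Part B and of amylase/lipase draws in both parts.

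**2. What happens between Cycle 1 toxicity and the window (Protocol 5.4).**
- Dosing on Day 1 requires AST/ALT and bilirubin at Grade 1 (Table 5-3); otherwise both drugs are withheld.
- Grade 3 non-hematologic laboratory values lead to a dose reduction; amylase and lipase are excluded.
- Patients with treatment-related Grade 4 toxicity "will withdraw from treatment definitively without further reduction", with amylase and lipase excepted in that paragraph.
- Immune-related Grade 3–4 liver elevations end treatment (Table 7-2).

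For AST, ALT and bilirubin these rules select patients, or change their dose, on the basis of Cycle 1 toxicity. For amylase and lipase, Table 5-3 allows re-treatment up to Grade 3, so the same mechanism largely does not operate. A later paragraph of 5.4 stops treatment for any treatment-related Grade 4 toxicity without repeating the amylase/lipase exception; the two statements must be reconciled.

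**3. Does Cycle 2 Day 1 recover late Cycle 1 toxicity?** If Day 1 slips by more than 3 days, its assessments move to the restart day (Protocol 5.4). SAP 16.1 runs a cycle to the day before the next Day 1. Assuming that definition also governs 19.3, a liver elevation that delays Cycle 2 this way is counted in Cycle 1, and the Day 1 liver values of patients dosed per protocol meet the Grade 1 gate. That leaves 2 of the 4 window draws (C2D15, C3D15) able to show a higher liver grade without postponing a cycle.

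**4. Direction of the effect.** An illustrative simulation used 400,000 patients per scenario, with a latent normal toxicity score per cycle cut into grades. All parameters are assumptions: exposure slope 0 to 0.8 per SD; stopping at Cycle 1 Grade ≥3 or ≥4; a downward shift of 0 or 0.7 in continuing patients with Cycle 1 Grade ≥2, standing for a dose reduction; within-patient correlation 0 or 0.4; 15% unrelated dropout. Spearman correlation of Cycle 1 exposure with worst grade:

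| Exposure effect | Cycles 1–3, all patients | Cycles 2–3, entrants to Cycle 2 | Scenarios |
|---|---|---|---|
| Equal in all cycles | 0.43–0.64 | 0.36–0.60 | 12 of 12 lower |
| Mainly Cycle 1 | 0.43–0.48 | 0.15–0.28 | 6 of 6 lower |
| Mainly delayed | 0.31–0.52 | 0.48–0.62 | 12 of 12 higher |

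The restriction weakened the relation in all 18 early or constant scenarios and strengthened it in all 12 delayed ones.

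**The case against.** The best defence is that these are descriptive box plots with no test, threshold or decision attached, and that a Cycles 2–3 window guarantees that both Cmax measurements precede the outcome. Both points stand. The second is a good reason to keep the plot as a supplement. It does not require dropping Cycle 1, because grades drawn after the relevant dose also follow exposure.

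A reader might infer four stronger things that the documents do not support.

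- **That this is the only exposure–safety analysis.** The QTcF plots are exposure–safety analyses on Cycle 1 data. Protocol 11.6.4.5 adds: "The relationship between PK disposition and clinical response, PDy, QTcF variations, safety and genetic variations in DMET genes will be analyzed by regression methods". The synopsis plans a pooled exposure/response analysis, reported separately. These are the only laboratory-grade exposure plots specified in SAP 19.3, and no more than that.
- **That any relation is biased toward none.** Step 4 shows that the direction depends on when the effect occurs.
- **That selection affects all five parameters alike.** The hold and reduction argument is mainly about AST, ALT and bilirubin.
- **That Cycle 1 toxicity disappears from reporting.** SAP 18.3 gives worst grade overall and by cycle, and SAP 19.2 lists individual PK parameters. What is missing is the planned link between Cycle 1 grade and exposure.

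The draw shares are also not effect sizes: they count scheduled visits, not patients, events or bias. Unscheduled values count toward worst grades (SAP 7.4), but those taken in Cycle 1 fall outside the window too.

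**Conclusion.** The concern holds in limited form. The window omits 56% of scheduled post-dose liver draws through Cycle 3 Day 15 in Part A, 43% in Part B, and 43% of amylase and lipase draws in both parts, together with all patients who stop in Cycle 1. For the three liver parameters, an early or constant exposure–toxicity relation may be attenuated; a mainly delayed one would not be. The omission follows directly from the documents. The attenuation is a plausible consequence whose size rests on assumed parameters, and the documents do not say how many patients stop before Cycle 2. Because the analysis is exploratory and Cycle 1 grades are reported elsewhere, this is a cheap improvement, not a threat to the trial's conclusions.

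**What to change.** In SAP 19.3:

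- Define the main outcome as the worst post-dose grade from first dose to the end of Cycle 3, in all patients with the Cmax value and at least one post-dose laboratory result.
- For Cmax at Cycle 1 Day 8, count only samples taken after the Day 8 dose. Starting the window at Day 8 itself would admit a sample drawn before the exposure.
- Keep the Cycles 2–3 plots as a supplement and state beside each how many patients have no Cycle 2–3 value.

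This takes a short SAP edit and no new data. The cost is up to 10 further exploratory plots per study part, and early laboratory changes not caused by the drug will also be counted.
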